5.3.3 Contraception

Females of child-bearing potential who engage in heterosexual intercourse during the trial must utilize one of these approved methods for contraception:

- Oral Hormonal Contraception
- Patch Contraception
- Hormonal Ring
- Intrauterine Device (IUD)
- Contraceptive Implantation
- Contraceptive Shot
- Barrier Method, including:
 - Male Condom
 - Female Condom
 - Diaphragm
 - Cervical Cap with spermicide
 - Contraceptive Sponge
 - Spermicide

5.4 Screen Failures

Participants who fail the initial screening process will be notified as soon as the screen failure is recognized. Participants that failed the screening process due to failing to meet the inclusion criteria or meeting exclusion criteria may be rescreened at a later date if the reason for their original exclusion no longer applies, or if a protocol amendment changes the eligibility criteria that caused the original screen failure. A minimum of 30 days should occur between re-assessing eligibility. Participants that were excluded because they demonstrated evidence of suicidality on the C-SSRS at the original screening will not be permitted to rescreen.

Participants that were excluded due to an insufficient NMS burden threshold under a previous protocol version will be permitted to rescreen once, if the original screening MDS-UPDRS Part I score was ≥ 9 , regardless of the source of their original score (i.e., “Patient Alone” or “Patient + Informant”). Additionally, participants that were excluded at the original screening due to an insufficient NMS burden under a previous protocol version and had an MDS-UPDRS Part I score of 7 or 8 will be permitted to rescreen once if the source of their original MDS-UPDRS Part I score was “Patient Alone”, and they now have the ability to have “Patient + Informant” source of data. Participants that were excluded due to an insufficient NMS burden with MDS-UPDRS Part I scores ≤ 6 will not be permitted to rescreen.

5.5 Strategies for Recruitment and Retention

The majority of participants for the study are expected to be drawn from existing patient populations at the clinical sites/services after medical record review. However, sites may choose to utilize recruitment aids such as IRB-approved advertisements.

The Sponsor will assign a Clinical Research Associate (CRA), also known as a study monitor, to each site. Enrollment for each site will be closely monitored by the CRA via Pre-screening logs that will be reviewed on a regular basis. If needed, the CRA will work closely with the site to identify recruitment barriers and find solutions to overcome these hurdles.

A variety of strategies are being utilized to promote participant retention. The study design facilitates retention as most study activities can be performed in the participant’s home, thereby reducing participant and caregiver burden. Additionally, participants will receive stipends to compensate for the travel and time burden associated with participation in the study. Study sites are encouraged to have continuous communication with the study participant and study partner outside of the defined protocol visits, in the manner most accommodating to them, to assist with rapport and retention. Participant retention will also be closely monitored and the CRA will work with the site to identify solutions should retention issues arise.

6 Study Intervention

Intended Use: The TNM™ Device is intended to stimulate the vestibular system via external ear canals using software-controlled thermal waveforms.

6.1 Study Intervention Administration

The generation 3.2 TNM™ device was granted market entry by the FDA as a Class II medical device indicated for the home-use prevention of episodic migraine in adolescent and adult patients 12 and older.

The generation 4.0 Device will be utilized in this study. See Scion TNM™ 4.0 Information for Use brochure for more details. The device has been designated as non-significant risk (NSR) by the FDA for studies in PD.

For treatment, all participants will recline on a wedge pillow (provided by SNS) to position the horizontal semicircular canal in the optimal orientation for maximal caloric effect. Participants will start and stop the device with a single push button to activate a run. Starting and stopping the device requires an extended push (2 seconds) to avoid false activations due to short button pushes. The LED display provides a “countdown” icon to provide the participant with feedback on how the treatment session is proceeding. The display also tells the participant how many treatments are left within the prescription period. The device provides an audio alert that denotes the start and completion of a treatment run. The same visual and auditory information will be presented to the two treatment arms.

Device treatment does not require active engagement of the participant. Therefore, participants will be told that they should feel free to read, watch television or rest so long as they remain in the supine position for the duration of treatment. Participants may be provided items to make the treatment time more conducive to reclining leisure activities such as reading, watching tv, etc. An example of such an item would be prism glasses to enable reading, if desired, while lying supine during a treatment.

Participants will be asked to treat twice daily. Each treatment duration is roughly 19 minutes. Participants will only wear the device when administering a treatment. Participants will be instructed to self-administer treatments in the on-state and at a time when they do not anticipate interruptions that would require them to pause a treatment.

No reference to caloric vestibular stimulation or “CVS” will be made with study participants. The device will be referred to as a brainstem neuromodulation Device, and the specific mechanism of action will not be disclosed to participants. Additional details regarding device description can be

found in site provided guidance documents.

All participants will be told that they may or may not benefit from device therapy in terms of reduction in PD-related symptoms. All participants will be told that participants in both treatment arms may or may not sense slight pressure from the earpieces, a warming or cooling sensation, slight nausea or dizziness or noises from the Device. To mitigate risk of falls that may result from orthostatic hypotension, participants will be instructed to take their time getting up after a treatment and to avoid going directly from a supine position to standing up and moving around.

As part of the Informed Consent, participants will be told that they will receive up to 20 weeks total of the treatment that has been shown to be most effective for treating symptoms in PD should they agree to participate in the open label extension (OLE).

Study Partners and site personnel should encourage participant adherence to device usage throughout duration of the trial but maintain a neutral position regarding efficacy to promote scientific integrity of the study.

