1.1.2 Objectives

Randomized Clinical Trial (RCT): STEM-PD (SNS-PD-002)

Primary Objectives: The primary objective of the RCT will be to test the hypothesis that TNM™ treatments provide safe and effective therapy for the reduction of non-motor symptom burden in participants with PD.

Secondary Objectives: This study will seek to establish whether TNM™ treatments provide adjuvant therapeutic effectiveness beyond that observed with dopamine replacement therapies (DRTs) to (1) provide global benefits, (2) improve activities of daily living related to motor function, (3) provide clinically meaningful change (4) improve motor symptoms and (5) improve quality of life (QoL) for participants with PD.

Safety Objectives: This study will seek to establish the safety of TNM™ by monitoring adverse events by evaluating whether TNM™ is associated with a worsening of balance, functional

mobility and gait in participants with PD.

Exploratory Objectives: This study will seek to establish the effectiveness of TNM™ therapy for treating specific non-motor symptoms (NMS) and in treating motor complications from oral dopamine replacement therapies. Outcomes will evaluate the clinical meaningfulness of symptomatic improvements, explore the temporal kinetics of motor symptom response to treatment, evaluate the potential of Device therapy to improve gait and to establish the health economics for TNM™ therapy.

Open Label Extension OLE: STEM-PD-OLE (SNS-PD-003)

The purpose of the OLE study is to gather the additional data needed to support reimbursement.

Objectives: The OLE has been designed to address the following objectives: (1) demonstrate reproducibility of the results from the RCT in a second cohort (i.e. all participants, including recipients of active treatment and recipients of passive treatment in the RCT will receive active treatment in OLE), (2) evaluate effectiveness of the Device treatments over an extended treatment interval, (3) collect additional data to support health economic benefits, (4) confirm clinical meaningfulness of RCT results and (5) evaluate the potential for the device to slow disease progression.

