The results from the single-site RCT study provide strong evidence to support the safety and effectiveness of TNM™ Device treatments for managing the symptoms associated with PD. TNM™ Device treatments in this study utilized the same time-varying waveform and BID schedule as was used in a pivotal study that demonstrated TNM™ is a safe and effective

prophylactic for episodic migraine. The study described herein will utilize the same active treatment waveform and BID treatment regimen as were used in these previous studies.

In this study, participants will treat for 12 weeks (84 days) rather than 8 weeks (56 days), as was the case for the single-site RCT study. The selection of a longer treatment interval was based on the finding that the treatment response, including measures of NMS burden, did not reach an asymptote during the 8 weeks of treatment. These results suggest that additional gains may be obtained with longer treatment intervals. Notably, 12-week treatment intervals were shown to be safe for the indication of episodic migraine, and there has been no evidence from a small crossover study in PD that treatment intervals of 12-16 weeks of treatments increases the risk of device-related AEs relative to 8 weeks. The treatment interval in this study will be limited to 12 weeks to minimize confounding variables that may arise with participants changing concomitant medications.

The primary goal of this study is to replicate the results obtained from the PD single-site RCT in a multicenter RCT. As such, this study will focus on comparing an active treatment to a passive treatment.

4.4 End of Study Definition for RCT:

Participants will continue to be enrolled in the RCT until at least 184 participants have randomized. All other study participants that have been randomized into the RCT at this point will be allowed to continue in the RCT and enroll in and complete the OLE. The RCT will end when the final participant has completed the end of treatment assessment, at which point, the RCT will be closed out and analysis will occur.

4.5 End of Study Definition for OLE:

The end of study for the OLE will be considered complete when participants who have enrolled in the OLE are no longer being examined or the last participant's last study visit has occurred at week 52 (day 365 +/- 3 days) and or early termination has occurred.

5 Study population

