7.8.2.1. Statistical Significance

The null hypothesis is that 12 weeks of active tvCVS treatments during the OLE will yield an equivalent change in the passive-active treatment group of NMS burden as that which occurred in response to passive treatment during the RCT. The alternative hypothesis is that the passive-active treatment group will demonstrate a greater reduction of NMS burden after 12 weeks of active tvCVS treatment during the OLE than occurred after 12 weeks of passive treatment during the RCT. Rejection of the null hypothesis will indicate that the intervention was successful. The threshold to determine statistical significance will be set at $\alpha = 0.05$ based upon a 1-tailed test.

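### Consent presents the extension treatment as already shown to be most effective, adding an avoidable expectation cue to the OLE's uncontrolled primary comparison

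*Protocol*

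**What the plan says.** Protocol 6.1 describes what participants hear as part of informed consent: if they agree to join the extension, "they will receive up to 20 weeks total of the treatment that has been shown to be most effective for treating symptoms in PD". The 20 weeks are the two OLE treatment periods, 12 + 8.

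The same section also says: "All participants will be told that they may or may not benefit from device therapy". Study partners and site personnel are to encourage adherence but "maintain a neutral position regarding efficacy to promote scientific integrity of the study". It withholds the mechanism of action and any reference to caloric stimulation.

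On the state of the evidence, Protocol 1.1.2 says the RCT will "test the hypothesis that TNM™ treatments provide safe and effective therapy for the reduction of non-motor symptom burden". Protocol 4.3 opens with "The results from the single-site RCT study provide strong evidence to support the safety and effectiveness" of the device, and then states: "The primary goal of this study is to replicate the results obtained from the PD single-site RCT in a multicenter RCT".

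On timing, Protocol 4.1 starts each participant's OLE directly after that person's own RCT completion. Under 4.1.2 the OLE baseline visit is on day 113 or within 3 days. Protocol 4.4 says: "The RCT will end when the final participant has completed the end of treatment assessment, at which point, the RCT will be closed out".

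OLE SAP 7.8.2 restricts the primary comparison to people who had passive treatment in the RCT. It sets their MDS-NMS change over days 29–113 against their change over days 113–197. OLE SAP 7.8.2.1 uses a one-sided 0.05 test and adds: "Rejection of the null hypothesis will indicate that the intervention was successful". OLE SAP 7.8.2.2 treats statistical significance as sufficient for clinical meaning.

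**The concern.** Participants are given as settled a superiority that this RCT is being run to establish. The protocol otherwise manages expectation with care. RCT SAP 7.10.4 goes as far as recognising that the sponsor and device names could alter what participants expect, keeps them off consent forms where ethics bodies allow, and plans separate models by whether the sponsor name was disclosed. A direct statement about efficacy is a plainer cue than a company name, yet no safeguard or sensitivity analysis addresses it.

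The comparison at stake is the OLE primary one. The outcome is a rater-completed symptom scale built from frequency and from distress or disturbance. In the first period the participant does not know which treatment is being given. In the second, the participant knows it is the one described at consent as most effective. Any improvement that follows from that description counts toward the device, and the result is intended to support reimbursement and clinical adoption.

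**Working it through.** **1. Does the statement come before the trial's result?** Protocol 6.1 does not say whether it means the RCT consent or the separate OLE consent, and the consent forms are not available.
- RCT consent: it is made before screening procedures, before any randomized data exist for that person.
- OLE consent: it is made at about day 113 of that person's participation. The RCT is closed and analysed only after the last randomized participant's end-of-treatment visit.

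Under both readings the statement precedes any result of this RCT.

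**2. What could the statement refer to?** Protocol 2.2.2 and 4.3 describe the earlier single-site RCT in Parkinson's disease: 8 weeks of treatment, device Generation 3.1, same waveform and twice-daily schedule. The present trial uses 12 weeks and Generation 4.0 and names replication as its primary goal. The phrase therefore has a source, but it presents a finding still to be replicated as established.

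**3. How does the cue enter the OLE contrast?**

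| | RCT period (days 29–113) | OLE period (days 113–197) |
|---|---|---|
| Treatment | passive | active |
| Participant's knowledge | blinded | open label |
| Consent description | may or may not benefit | may or may not benefit, and most effective |
| Concurrent control in this analysis | none | none |

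Even if the statement is heard before the RCT, it describes the extension treatment, and only in the extension does the participant know that this is what is being given. The cue is therefore unequal between the two periods, and it points in the direction of the one-sided alternative.

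**4. How sensitive is the OLE test to any shift?** Inputs are from OLE SAP section 4: n = 74 (83 × 0.9 = 74.7, taken as 74), difference 2.64 points on MDS-UPDRS Part I, SD 5.32, alpha 0.05, paired t-test.
- Standard error = 5.32/√74 = 0.618.
- Noncentrality = 2.64/0.618 = 4.27 on 73 degrees of freedom.
- Power = 98.8% two-sided and 99.5% one-sided. The plan's figure of more than 98% is reproduced.
- Smallest observed mean difference significant at one-sided 0.05: 1.666 × 0.618 = 1.03 points, or 1.03/5.32 = 0.19 SD.

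With no true device effect and an **assumed** shift from any non-device source, the chance of declaring success (noncentral t, noncentrality = shift/0.618) is:

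| Assumed shift (points) | Chance of declaring success |
|---|---|
| 0 | 5.0% |
| 0.25 | 10.7% |
| 0.5 | 19.9% |
| 1.0 | 48.3% |

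This shows only that a test planned with this much power has little tolerance for bias. It does not measure the consent phrase. It also uses the plan's surrogate scale and paired t-test, whereas the endpoint is the MDS-NMS analysed by a mixed model.

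**The case against.** The strongest reply is that the phrase has a basis. An earlier randomized trial in Parkinson's disease found benefit, with blinded motor rating and allocation-guess data indicating that blinding held, and the protocol regards it as strong evidence. This stands in part. A reader might infer that the claim is unsupported altogether, and the documents do not bear that out. What remains is that one single-site trial awaiting replication is presented as settled.

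A reader might also infer that Protocol 6.1 contradicts itself. It does not, strictly. Saying an individual may or may not benefit is compatible with one treatment being better on average, and the neutrality instruction governs the conduct of partners and staff rather than consent content. It is a tension, though a real one if site staff deliver the statement while required to stay neutral.

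It is fair to say that any open-label before-and-after comparison carries expectation bias whatever consent says. The wording adds to that bias and is not its only source, and nothing in the documents separates the two. Expressing its effect as some share of an MDS-NMS minimal important difference would be a guess.

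Finally, a reader might infer that the phrase damages the RCT by prompting participants to guess their allocation. The documents do not support that. Both arms hear the same statement, both are told they may feel warming or cooling, other sensory cues are described as matched, and allocation is not disclosed.

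**Conclusion.** The point holds as a matter of consent wording and OLE interpretation. Before any result of this RCT, participants are told that the extension treatment is proven best. That adds an avoidable cue in the device's favour to a within-person contrast with no concurrent control, whose rejection is read as success.

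The size of the added bias cannot be estimated from the documents. The calculation shows only that, on the plan's own inputs, a mean difference of about 0.19 SD from any source reaches significance. The randomized contrast, which is the trial's main test of efficacy, is not directly biased.

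The conclusion rests on two assumptions: that the consent text matches the description in Protocol 6.1, and that participants know in the OLE that they are receiving the treatment so described.

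**What to change.** In Protocol 6.1 and the matching consent text, delete the clause claiming demonstrated superiority and replace it with neutral wording. For example: everyone in the extension receives the same study treatment for up to 20 weeks, and it is not yet known whether it works better than the other treatment in this study. Keep the existing advice that participants may or may not benefit.

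Rewording cannot help people who consented under the present text. For them, the OLE report should describe the primary contrast as uncontrolled and open to expectation effects, and should not present rejection of the null alone as evidence that the device worked.

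The cost is a protocol and consent amendment with ethics approval, and a slightly weaker retention message. Retention also rests on stipends, home-based activities and site contact (Protocol 5.5). Expectation bias from open-label treatment would be reduced, not removed.

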6.2 Preparation/Handling/Storage/Accountability

Study devices must be stored in a secure area with limited access. Storage rooms used for this purpose must have continuous locked access and only delegated research staff should be allowed to enter.

Upon receipt, the shipment of study devices will be inventoried. Any discrepancies or damaged shipments will be brought to the attention of the sponsor. Copies of the packing slips will be retained, and inventory will be documented on the Investigator Inventory Control Form located in the Investigator Site File for the study. The Sponsor and the Investigator are required to closely monitor the shipping, use, and final disposal of devices.

Investigators must also maintain complete, current, and accurate records of the receipt, use, or disposition of investigational devices. Delegated research staff should complete the Investigator Inventory Control Form whenever one of the following occurs: 1) devices are received from the Sponsor, 2) devices are dispensed to participants, 3) devices are returned from participants and 4) devices are shipped back to the Sponsor. In the case of a damaged or failed device, an Investigational Device Return Form should be completed, and the Sponsor immediately notified.

Upon completion or termination of the study (or the Investigator's part of the study), or at the sponsor's request, the Investigator is required to return to the Sponsor any remaining supply of the device, unless otherwise directed.

6.3 Device Randomization, Blinding, and Unblinding

The Generation 4.0 TNM™ device uses a bar code reader to import a prescription waveform. The use of the bar code aids blinding during randomization since the QR code is not readable by staff members. Bar codes will be printed and placed in sealed envelopes and the treatment allocation will not be available to the site staff. Unblinding will only occur in response to a Serious Unexpected/Unanticipated Device Event and requires written permission by the study sponsor [see below].

Packets containing 4 sealed envelopes with the printed bar codes for randomization assignments

will be provided. Each batch will contain two active treatment and two passive treatment assignments. The envelopes will be randomly shuffled by an agent not involved with the study. A given packet must be completed before the next packet is opened.

For randomization, after eligibility is confirmed and documented, delegated study staff will select an envelope from the packets, scan the bar code in the envelope and then store the barcode on the randomization source log. Study staff will load the treatment onto the device, record the device number allocated to the participant and will train the participant according to the training script provided. The first treatment will be performed at the participant's home to maintain blinding of the study staff.

All study staff will be blind to treatment allocation and participants will be told at informed consent, and all subsequent visits, that they should not discuss their treatment experience with the study staff. Confirmation that the study staff remain blinded to treatment allocation will be documented at each visit. If a study staff member directly responsible for assessment or safety evaluation becomes unblinded, they will no longer be eligible to complete the delegated study assessments per the protocol for that participant. Participants will be told that pain should not be associated with treatment, and if they do experience pain, that they should stop treatment and contact the study staff immediately and/or seek medical attention if necessary.

Study staff will not have access to the allocation treatment on site, as treatment allocation is not required to treat any potential adverse events. Unblinding at the study sites will only occur in the case of a SADE (serious adverse event at least possibly related to the device) or UADE (serious and unanticipated/unexpected adverse events at least possibly related to the device) that also require cessation of device treatment. If this situation seems likely, the Unblinding Investigator, noted in the Delegation of Authority Log, should contact SNS at the contact information below to request approval to unblind and obtain the assigned treatment allocation. The unblinded Investigator will not be allowed to complete assessments for that participant if they become unblinded. The safety event will be reported as required by this protocol. Should treatment allocation information be required for handling of an AE, a CRF providing the details of the incident will be completed.

Unblinding Sponsor Contact:
[name]
[contact]
24-hour number: [contact]

